6.	REFERENCES	56
7.	AMENDMENTS	56
8.	ATTACHMENTS AND APPENDICES	57

ABBREVIATION

7-COOH-CBD		7-carboxy-CBD
7-OH-CBD	-	7-hydroxy-CBD
ABCL	-	Adult Behavior Checklist
AEDs	-	Antiepileptic Drugs
AEs	-	Adverse Events
ANCOVA	-	Analysis of Covariance
ALQ	-	Above Limit of Quantification
ATC	-	Anatomical Therapeutic Chemical
BDRM	-	Blinded Data Review Meeting
BLQ	-	Below Limit of Quantification
CBCL	-	Child Behavior Checklist
CBD	-	Cannabidiol
CGIC	-	Caregiver Global Impression of Change
CGICSD	-	Caregiver Global Impression of Change in Seizure Duration
CI	-	Confidence Interval
CMH	-	Cochran–Mantel–Haenszel
CRF	-	Case Report Form
C-SSRS	-	Columbia-Suicide Severity Rating Scale
CWS	-	Cannabis Withdrawal Scale
ECG	-	Electrocardiogram
IGF-1	-	Insulin-like Growth Factor-1
IMP	-	Investigational Medicinal Product
ITT	-	Intention to Treat
IVRS	-	Interactive Voice Response System
LGS	-	Lennox-Gastaut Syndrome
LOCF	-	Last Observation Carried Forward
MAR	-	Missing at Random
MedDRA	-	Medical Dictionary for Regulatory Activities
MI	-	Multiple Imputation
MNAR	-	Missing Not at Random
NOCB	-	Next Observation Carried Backward
NRS	-	Numerical Rating Scale
OLE	-	Open Label Extension
PCWS	-	Pediatric Cannabinoid Withdrawal Scale

PGIC	-	Physician Global Impression of Change
PK	-	Pharmacokinetics
PP	-	Per Protocol
QOLCE	-	Quality of Life in Childhood Epilepsy
QOLIE-31-P	-	Quality of Life in Epilepsy, version 2
RM	-	Rescue Medication
SAP	-	Statistical Analysis Plan
SGIC	-	Subject Global Impression of Change
SGICSD	-	Subject Global Impression of Change in Seizure Duration
SOC	-	System Organ Class
SCQ	-	Social Communication Questionnaire
TAND	-	TSC-associated Neuropsychiatric Disorders
TEAE	-	Treatment Emergent Adverse Event
TSC	-	Tuberous Sclerosis Complex
ULN	-	Upper Limit of Normal
Vineland-II	-	Vineland Adaptive Behavior Scales, Second Edition

1. INTRODUCTION

This statistical analysis plan (SAP) documents the statistical reporting to be performed for trial GWEP1521.

This SAP has been prepared based on the following protocol:

- Protocol GWEP1521 (Version 8, dated 23rd April 2019).

1.1 Rationale

Tuberous sclerosis complex (TSC) is a genetic disorder characterized by the formation of nonmalignant tumors (tubers) in multiple organ systems. The clinical signs of TSC arise as a result of inactivating mutations in either of two tumor suppressor genes: *TSC1* (located on chromosome 9q34.13) or *TSC2* (located on chromosome 16p13.3). Thus, inactivating mutations in *TSC1* and *TSC2* lead to inadequate suppression of mTOR signaling, resulting in abnormal cellular growth and tumorigenesis.

Mutations in *TSC1* account for approximately 15% of all cases of TSC whilst approximately 70% of all cases are due to mutations in *TSC2*; ~15% of TSC patients have no identifiable mutation in the coding regions of either gene. Generally, *TSC2* mutations result in a more severe disease phenotype compared with *TSC1* mutations. The birth incidence of TSC is estimated to be 1 in 6,000 with approximately 50,000 individuals in the United States and 1 million individuals worldwide affected.

Tumors in TSC patients can occur in any major organ yet develop primarily in the brain, eyes, heart, kidney, skin and lungs.

Epileptic seizures are the most common clinical manifestation of TSC, affecting more than 70% of patients. Seizure onset occurs within the first year of life in approximately two-thirds of TSC patients and occurs within the first 3 years of life in 80% of TSC patients. The onset of epilepsy in TSC commonly manifests as focal motor seizures, which in approximately one-third of TSC patients coexist with infantile spasms.

Virtually all TSC patients with infantile spasms and approximately half of all epileptic TSC patients without them develop multiple seizure types, including complex focal seizures (with or without secondary generalization), generalized tonic-clonic seizures, atonic seizures, and atypical absences. Although infantile spasms resolve with time, the frequency and severity of other seizures tend to increase throughout early childhood and nearly two-thirds of TSC patients develop medically intractable epilepsy, including Lennox-Gastaut syndrome.

Early management of seizures is therefore important in preventing subsequent epileptic encephalopathy and in reducing the associated cognitive and neuropsychiatric consequences.

The pharmacological therapies currently available for TSC-associated epilepsy often produce serious adverse effects, and a significant proportion of patients (37–63%) become resistant to treatment. Consequently, there is a clear need for new, efficacious pharmaceutical treatments for refractory epilepsy. Given the limitations of current synthetic antiepileptic drugs (AEDs), it has been suggested that CBD should be tested for anticonvulsive efficacy in randomized controlled clinical trials, especially in infantile epileptic syndromes. Although there are no published reports to date investigating the efficacy of CBD for seizures in TSC patients, a recent parent survey has reported that 84% of children with treatment-resistant epilepsy experienced a reduction in seizures whilst taking CBD-enriched cannabis, with over half of those reporting >80% reduction in seizure frequency.

The CBD-enriched cannabis was behaviorally well tolerated and children often experienced improved sleep, increased alertness, and better mood.

2. TRIAL OBJECTIVES

The protocol defined the trial objectives as:

2.1 Primary Objective

Blinded Phase:

To evaluate the efficacy of GWP42003-P as add-on therapy in reducing the frequency of seizures when compared with placebo in patients with TSC.

Open-label Extension:

To evaluate via the adverse events (AE) profile the long term safety and tolerability of GWP42003-P as add-on therapy in children and adults with TSC who experience inadequately-controlled seizures.

2.2 Secondary Objectives

Blinded Phase:

- To evaluate the effect of GWP42003-P compared with placebo on antiepileptic measures.
- To evaluate the effect of GWP42003-P on growth and development (in patients less than 18 years old) compared with placebo.
- To evaluate the effects of GWP42003-P on quality of life compared with placebo.
- To evaluate the safety and tolerability of GWP42003-P compared with placebo.

Open-label Extension:

- To evaluate the long term effects of GWP42003-P, as add-on therapy, on antiepileptic measures.
- To evaluate the long term effect of GWP42003-P on growth and development (in patients less than 18 years old).
- To evaluate the long term effects of GWP42003-P on quality of life.
- To evaluate the long term safety and tolerability of GWP42003-P.

2.3 Exploratory Objectives

Blinded Phase:

- To evaluate the effect of GWP42003-P on TSC-associated neuropsychiatric disorders (TAND), including cognitive and behavioral function and autistic features compared with placebo.
- To determine the pharmacokinetics (PK) of CBD, and its major metabolites following single and multiple doses of GWP42003-P.
- To evaluate the effects of GWP42003-P on plasma concentrations of concomitant AEDs, if applicable.

Open-label Extension:

- To evaluate the long term effect of GWP42003-P on TAND, including cognitive and behavioral function and autistic features compared with placebo.

3. INVESTIGATIONAL PLAN

3.1 Trial Design

This multicenter trial consists of a randomized, placebo-controlled, double-blind phase followed by an open-label extension (OLE) phase.

Blinded Phase:

The blinded phase of the trial is a randomized, double-blind, parallel-group, 16-week comparison of two doses of GWP42003-P vs. placebo. Patients will complete a 1-week screening period and a 4-week baseline period before they are randomized to receive either 25 mg/kg/day GWP42003-P, 50 mg/kg/day GWP42003 P or placebo. Randomization will be stratified by age according to the following ranges: 1–6, 7–11, 12–17 years and 18–65 years. Patients will begin a 4-week dose escalation period, titrating up to their assigned dose, before continuing on a stable dose of blinded Investigational Medicinal Product (IMP) for 12 weeks.

Dose escalation for each patient is subject to the investigator's assessment of safety and tolerability. If a dose becomes poorly tolerated, the investigator may consider temporarily or permanently reducing the dose for the remainder of the trial.

Following completion of the blinded phase, patients will be invited to continue to receive GWP42003-P in an OLE.

Those patients opting not to enter the OLE will complete a 10-day taper period (down-titrating 10% per day for 10 days).

Open-label Extension Transition:

In order to maintain consistent exposure to IMP and maintain the integrity of the blind, patients will enter a 2-week blinded transition to the OLE. OLE IMP will be titrated up to 25 mg/kg/day whilst blinded IMP is simultaneously tapered down to zero. All patients will complete the transition and enter the OLE taking 25 mg/kg/day GWP42003-P:

- Patients from the placebo arm will titrate up to 25 mg/kg/day GWP42003-P.
- Patients from the 25 mg/kg/day GWP42003-P arm will continue to take 25 mg/kg/day GWP42003-P.
- Patients from the 50 mg/kg/day GWP42003-P arm will taper down (10% per day) to 25 mg/kg/day GWP42003-P.

Open-label Extension:

The OLE consists of a 3-week titration period followed by a maintenance period and a 10-day taper period. The initial OLE period will last for a maximum of 1 year.

Following titration according to the titration schedule, patients will continue with their optimal GWP42003-P dose. However, investigators may decrease the dose if a patient experiences intolerance, or increase the dose to a maximum of 50 mg/kg/day if required for better seizure control, until the optimal dose is found.

3.2 Definition of Sample Size

Blinded Phase:

A total of 210 patients will be enrolled. The 210 patients will be randomly allocated to 1 of 4 treatment arms (GWP42003-P 25 mg/kg/day, GWP42003 P 50 mg/kg/day, placebo 25 mg/kg/day dose volume equivalent, or placebo 50 mg/kg/day dose volume equivalent) at a 2:2:1:1 ratio. The placebo arms will be pooled for the analyses of efficacy.

If it is assumed that patients in the placebo arm will experience a mean reduction in seizure frequency of 15% (from baseline), patients receiving GWP42003-P will experience at least a 50% reduction in seizures and a common standard deviation of 60%, then this sample size of 70 patients per arm will be sufficient to detect a difference in response distributions with 90% power. This test is based on a two-sided non-parametric Mann-Whitney-Wilcoxon test for continuous response data with a 5% significance level.

Open-label Extension:

All patients who wish to continue on IMP following the blinded phase.

3.3 Efficacy and Safety Endpoints

3.3.1 Primary Efficacy Endpoint

Blinded Phase:

The primary endpoint is the change in number of TSC associated seizures* during the treatment period (maintenance and titration) compared to baseline in patients taking GWP42003-P compared with placebo.

*Primary endpoint TSC-associated seizures include: focal motor seizures without impairment of consciousness or awareness; focal seizures with impairment of consciousness or awareness; focal seizures evolving to bilateral generalized convulsive seizures and generalized seizures (tonic-clonic, tonic, clonic or atonic) that are countable.

Open-label Extension:

The safety of GWP42003-P will be evaluated by assessing the incidence, type and severity of AEs.

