5. STATISTICAL METHODS

5.1 General Considerations

In all tables, listings and figures for the double-blind phase, the trial medications will be referred to and labelled as per Table 1.

Table 1 Blinded Phase Trial Treatments

Endpoint	Actual Treatment	Treatment Label
Efficacy	Pooled Placebo	Placebo
Safety	25 mg/kg/day Placebo	Placebo 25 mg/kg
	50 mg/kg/day Placebo	Placebo 50 mg/kg
All	25 mg/kg/day GWP42003-P	25 mg/kg
All	50 mg/kg/day GWP42003-P	50 mg/kg

For safety tables where placebo is split by dosing volume, an additional Pooled Placebo column will be included.

For OLE tables, columns will be included for treatment received during the double-blind phase (GWP42003-P or placebo, i.e. not split by dose) and overall.

In all tables, listings and figures, the trial visits will be referred to and labelled as per Table 2.

Table 2 Trial Visits

Actual Visit	Visit Label
Visit 1: Screening	Day -35
Visit 2: Day -28, baseline visit	Day -28
Visit 3: Day 1, Randomization	Day 1
Visit 4: Day 15	Day 15
Visit 5: Day 29	Day 29
Visit 6: Day 43	Day 43
Visit 7: Day 57	Day 57
Visit 8: Day 71, Telephone	Day 71
Visit 9: Day 85	Day 85
Visit 10: Day 113	End of Treatment
Visit 11: Day 123	End of Taper
Visit 12: Day 151	Safety Follow-Up
Visit B1: Day 1, Enrollment	OLE Day 1
Visit B2: Day 15	OLE Day 15
Visit B3: Day 36	OLE Day 36
Visit B4: Day 92	OLE Day 92
Visit B5: Day 141, Re-stocking of supplies	OLE Day 141
Visit B6: Day 183	OLE Day 183
Visit B7: Day 232, Re-stocking of supplies	OLE Day 232
Visit B8: Day 274	OLE Day 274
Visit B9: Day 323, Re-stocking of supplies	OLE Day 323
Visit B10: Day 365	OLE End of Treatment
Visit B11: Day 375	OLE End of Taper
Visit B12: Day 389	OLE Post-taper Safety Telephone Call
Day 403	OLE Follow-Up

Unless stated otherwise, continuous variables will be summarized showing the number of non-missing values (n), mean, standard deviation, median, minimum and maximum and categorical variables will be summarized showing the number and percentage of patients falling in each category. For continuous summaries of seizure frequency, the lower and upper quartiles will also be presented.

Minimum and maximum values will be presented to the same decimal precision as the raw data. Mean and median will be presented to one more decimal place than the raw data, and standard deviation to 2 more decimal places than the raw data. Percentages will be presented to one decimal place.

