5.1.4 Interim Analysis

No formal interim analysis is to be conducted in this trial. However, interim reporting of the OLE may be required to support regulatory filings. This SAP contains details for the final reporting of the double-blind and OLE phases of the trial. For interim reporting of the OLE,

the rules described in the SAP will be followed. However, only a subset of outputs including OLE data may be required to support regulatory filings.

If interim reporting of the OLE is required, then only data available up to and including the date of the data cut will be included. The below section describes how data will be selected for the interim reporting.

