Where X corresponds to the treatment period estimate, or GWP42003-P ratio, and Y corresponds to the baseline period estimate, or placebo arm ratio.

Primary efficacy analysis will be performed using the ITT analysis set.

TSC-associated seizure frequency (28-day average) and percentage change in seizure frequency will also be presented using summary statistics. Percentage change from baseline in TSC-associated seizure frequency will be calculated as:

$$((\text{Frequency during the treatment period} - \text{Frequency during baseline}) \div \text{Frequency during baseline}) \times 100$$

The frequency during each period will be based on 28 day averages and calculated as:

$$(\text{Number of seizures in the period} \div \text{Number of reported days in IVRS in the period}) \times 28$$

For the TSC-associated seizure endpoints only, if patients are randomized with no TSC-associated seizures during the baseline period then the percentage change from baseline will be calculated as:

$$(\text{Frequency during the treatment period} + 1) \times 100$$

Open-label Extension:

The primary endpoint for the OLE is the safety of GWP42003-P, evaluated by assessing the incidence, type and severity of AEs. Data will be presented as per Section 5.6.2.

However, percentage change from baseline in TSC-associated seizure frequency is considered a key secondary endpoint for the OLE.

In the OLE, seizures are recorded on a weekly basis rather than daily. Caregivers/patients are expected to call the IVRS system to record the number of seizure subtypes experienced every 7 days during the OLE. TSC-associated seizure frequency per 28 days will be calculated for each of the periods described in Section 5.5.1. All calls that take place during the period in question will contribute to the calculation of the average number of seizures per day in that period only.

The average number of seizures per day in the period will be calculated as the average of:

$$\text{Number of seizures reported} \div \text{Number of days since last IVRS call}$$

The number of days since the last call will be calculated as follows, and is dependent on whether the call took place <7, 7 or >7 days after the previous call (or after the date of OLE Day 1 in the case of the first call in the first period):

- If the call takes place exactly 7 days after the previous call, then the number of days since the last call will be 7.

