The total number of dosing days will be calculated for the OLE and presented along with a categorical summary of patients whose largest dose was 25 mg/kg/day or less and patients whose largest dose was over 25 mg/kg/day during the OLE treatment phase.

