5.6.2 Adverse Events

All reported AEs will be classified by system organ class (SOC), preferred term and lower level term using Version 19.1 of MedDRA.

Summaries will be presented by treatment arm as well as SOC and preferred term.

A blinded phase treatment emergent AE (TEAE) is defined as an AE with a start date on or after the first dose of IMP during the blinded phase up to and including the date of first dose of the OLE phase (OLE Day 1). An OLE phase TEAE is defined as an AE with a start date on or after the OLE Day 1. If an AE has a partial start date and it is unclear from the partial date (or the stop date) whether the AE started prior to or post first dose of IMP then the AE will be considered treatment emergent and if it is unclear which phase the event started, it will be assigned to both phases. If the start date of the AE is the same as the date of first dose of IMP from the blinded phase and the plausible relationship to IMP is marked on the CRF as "Prior to study medication" then the AE will not be considered treatment emergent.

An AE will be considered treatment-related if the plausibility relationship to trial medication is recorded on the CRF as 'yes'. If the data on plausibility relationship to trial medication is missing then the AE will be considered treatment-related.

An AE will be considered leading to permanent discontinuation of IMP if the action taken with IMP is recorded on the CRF as 'study medication stopped' or the outcome is recorded on the CRF as 'patient died'.

An AE will be considered leading to IMP dose reduction excluding permanent discontinuation if the action taken with IMP is recorded on the CRF as 'dose reduced', 'dose reduced temporarily' or 'study medication interrupted'.

An AE will be considered leading to temporary IMP dose reduction if the action taken with IMP is recorded on the CRF as 'dose reduced temporarily'.

An AE will be considered leading to permanent IMP dose reduction excluding permanent discontinuation if the action taken with IMP is recorded on the CRF as 'dose reduced'.

An AE will be considered fatal if the outcome is recorded on the CRF as 'patient died'.

The following summaries will be generated separately for the blinded and OLE phase (counts are by patient unless specified otherwise):

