2.3.3 Robustness to Withdrawn Patients

There were higher proportions of patients in each treatment arm that withdrew during the blinded phase treatment period when compared with placebo. In order to assess the robustness of the results, 2 analyses in the following sections are proposed.

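### The primary endpoint of the open-label extension, AE incidence, has no patient-time or cumulative-incidence measure, so its crude percentages can understate one-year risk, most of all at an interim cut

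*SAP*

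**What the plan says.** The OLE objective in SAP 2.1 is long-term: "To evaluate via the adverse events (AE) profile the long term safety and tolerability of GWP42003-P as add-on therapy". Section 3.3.1 sets the OLE primary endpoint: "The safety of GWP42003-P will be evaluated by assessing the incidence, type and severity of AEs". Section 5.5.2 repeats the endpoint, "The primary endpoint for the OLE is the safety of GWP42003-P, evaluated by assessing the incidence, type and severity of AEs", and refers to 5.6.2 for its presentation. There the rule is "The following summaries will be generated separately for the blinded and OLE phase (counts are by patient unless specified otherwise"; the general rule in 5.1 is "categorical variables will be summarized showing the number and percentage of patients falling in each category". The OLE safety analysis set (5.2.4) holds everyone with at least one OLE dose.

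Three features of 5.6.2 matter here:

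- By-event tables are planned for all, treatment-related, serious, non-serious and treatment-related serious TEAEs. They have no time denominator.
- The time-of-first-onset summary (OLE Table 11.6) bases percentages on patients with a visit or call in each period. Its last class is everything after Day 84. Onset is the AE start date minus the date of first dose of IMP, plus 1.
- An OLE TEAE starts on or after OLE Day 1. No end of the window is given.

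On exposure, 5.6.1 says "The total number of dosing days will be calculated for the OLE", but nothing links those days to the AE tables. The initial OLE lasts at most 1 year (3.1), while the seizure periods in 5.5.1 run to Day 420 and beyond. Section 5.1.4 adds that "interim reporting of the OLE may be required to support regulatory filings", using only data up to the cut.

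**The concern.** OLE follow-up is unequal by design: patients leave at different times, and a data cut truncates those still on treatment. A crude percentage gives a patient followed for three weeks the same weight as one followed for a year. Read against a long-term safety objective, it depends on the cut date and on dropout as well as on AE risk.

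The SAP already allows for time elsewhere. OLE seizures are split into 12-week periods and expressed per 28 days (5.5.1, 5.5.2), and rescue medication is expressed per 28 days (5.5.4.3). The OLE primary endpoint gets no comparable treatment in its main tables. At stake is how interim and final OLE safety figures are read, including any prepared for a filing.

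**Working it through.** The SAP states no OLE AE rate, OLE dropout or follow-up at a cut, so there is no figure of its own to reproduce.

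**Inputs.** From the SAP: 1-year initial OLE, interim cuts possible, last onset class after Day 84, Visit B4 at Day 92. Assumed: true one-year risk 20%; dropout at a constant rate, independent of AE risk; hazard either constant or early, with 80% of the cumulative hazard in the first 28 days.

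**Formula.** Crude % = sum over days of P(first AE that day) × P(still followed that day).

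**Interim cut, follow-up uniform over 0-12 months, no dropout**

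- Constant hazard: h = −ln(0.80) = 0.2231 per year. Crude = 1 − (1 − e^−h)/h = 1 − 0.20/0.2231 = 10.4%.
- Early onset: risk by Day 28 = 1 − exp(−0.8 × 0.2231) = 0.1635, leaving 0.0365 for later. The mean fraction still followed is about 1 − 14/365 = 0.962 before Day 28 and (337/365)/2 = 0.462 after. Crude ≈ 0.1635 × 0.962 + 0.0365 × 0.462 = 17.4%.

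**Final report, dropout d by one year, constant hazard.** With λ = −ln(1 − d), crude = h/(h + λ) × [1 − 0.80(1 − d)].

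- d = 10%: 0.2231/0.3285 × 0.28 = 19.0%.
- d = 40%: 0.2231/0.7340 × 0.52 = 15.8%.

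Day-by-day sums give the full range:

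| Report | Dropout by 1 year | Constant hazard | Early onset |
|---|---|---|---|
| Interim, uniform 0-12 months | 0% | 10.4% | 17.4% |
| | 20% | 9.7% | 17.2% |
| | 30% | 9.3% | 17.0% |
| Interim, uniform 3-12 months | 20% | 12.0% | 18.2% |
| Final | 10% | 19.0% | 19.7% |
| | 20% | 18.0% | 19.5% |
| | 30% | 16.9% | 19.2% |
| | 40% | 15.8% | 18.8% |

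If instead 80% of the hazard falls after Day 84, the interim figure with uniform 0-12 month follow-up and no dropout is 10.1%.

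**Does the onset table repair this?** The open class covers 365 − 84 = 281 of 365 days. With constant hazard and full follow-up, first events after Day 84 occur in 0.80^(84/365) − 0.80 = 0.950 − 0.800 = 15.0% of patients. If the denominator is everyone reaching Day 92, the table shows 13.9% (final, 20% dropout), 13.3% (final, 30%) and 7.5% (interim over 0-12 months, 20%). A patient seen once after Day 84 counts in full, so the interim shortfall remains.

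**Time origin and denominator of that table.** Section 5.1.2 expects OLE Day 1 to coincide with the blinded end-of-treatment visit, which is Day 113. If first dose of IMP is read literally as blinded Day 1, an OLE event in a patient who completed the blinded phase has onset at Day 113 or later and falls in the last class. The text also takes the denominator from the safety analysis set, whereas the table list assigns OLE Table 11.6 to the OLE safety analysis set.

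**The case against.** Patients with an event over patients treated is a valid description of observed incidence. The SAP never calls it a one-year risk and plans no AE test. Dosing days and discontinuations with reasons are reported alongside. Interim OLE reporting is only a possibility, perhaps with a subset of outputs. The OLE opens with a transition and titration, so early-onset AEs are plausible, and for those the shortfall is modest. All of this stands, and it limits the size of the point. It does not remove it, because the objective is long-term and no planned AE table estimates risk over time.

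A reader might infer stronger claims that the document does not support:

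- *That AEs are reported only as crude patient counts over everyone enrolled.* The by-event tables and the onset table's period-specific denominators contradict this.
- *That the blinded-phase AE comparison is distorted in the same way,* since the addendum (2.3.3) says "There were higher proportions of patients in each treatment arm that withdrew during the blinded phase treatment period when compared with placebo". That would require AE observation to stop at withdrawal. Section 5.6.2 sets no such cut-off: the window runs to OLE Day 1, with no end stated for patients who never enter the OLE. Table 2 has taper and follow-up visits to Day 151, which is 38 days after Day 113.
- *That an earlier-leaving OLE column will look safer.* Equal 20% risks with 10% and 30% dropout would show 19.0% and 16.9%, but the SAP gives no OLE dropout. Someone who leaves because of an AE is already counted, and the columns are descriptive. A calendar cut should affect the randomized former arms similarly.

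**Conclusion.** The point holds as a gap in how the OLE primary endpoint is summarized. The crude tables are not wrong as descriptions of what was observed. Read as long-term risk, they understate it when follow-up is unequal and censoring is independent.

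For an assumed 20% one-year risk, the relative shortfall at an interim cut over 0-12 months without dropout is about 48% (10.4/20) with a constant hazard and 13% (17.4/20) with early onset. At a final report with 10-40% dropout it is about 5-21% with a constant hazard and 1-6% with early onset. The effect is therefore large only for AEs that accrue over time and are reported at an early cut. The onset table does not fill the gap, and its time origin needs correcting in any case.

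**What to change.** Keep all the crude tables. For OLE Tables 11.1, 11.2, 12.1 and 12.3 (all TEAEs, serious TEAEs and TEAEs leading to discontinuation), at interim and final reports:

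- add patient-years at risk and the exposure-adjusted incidence rate, that is, patients with a first event per 100 patient-years to first event or end of window, with 95% CI;
- add Kaplan-Meier cumulative incidence at 3, 6 and 12 months with numbers at risk.

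In 5.6.2:

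- state the end of the OLE TEAE window, which the rate needs (Table 2 runs from end of treatment at Day 365 to follow-up at Day 403, a 38-day difference);
- count OLE onset from OLE Day 1, with the OLE safety analysis set as the base;
- split the class after Day 84 into 12-week periods, as is done for seizures.

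The cost is SAP wording and some added table columns and rows; AE start dates and dosing days are already derived. The downsides are that a single rate assumes a constant hazard, and that Kaplan-Meier is biased if leaving is related to AE risk. Both should therefore stand beside the crude counts.
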